Subjects will be 14-25 year old female athletes with AA (n= 145), EA (n=), and female non-athletic controls (n= 42). Because different kinds of physical activity have different effects on bone metabolism, we will enroll only endurance athletes (please see Inclusion Criteria).

For Specific Aims 7-8, 40 adolescent and young adult male athletes 14-21 years old, and 20 adolescent and young adult male non-athletes 14-21 years old will be studied. Eligibility will be assessed over the phone, and the study will include one visit only.

Participation of Children: We will enroll only female adolescents/young adults to optimize power and avoid issues arising from deficiencies of different predominant sex hormones in boys (testosterone) vs. girls (estrogen). Adolescents and young adults will be studied to determine effects on BMD and its predictors in a population that should be actively accruing bone.

Inclusion Criteria

(i) Females 14-25 years old: Our pilot data are reassuring in that young women 14-25 years old with hypothalamic amenorrhea are not adversely affected with estrogen use. In fact, in our prospective study, beneficial effects were observed both in young women 18-25 years old using oral estrogen, and in 14-18 year old adolescent girls using transdermal estrogen. We therefore feel that including girls in the 14-21 year age range will not be hazardous to their bone health. In fact, given the lack of data in this age group, it is important to study younger women and teenagers rather than extrapolate data from studies in adults to this younger population. Hormone dynamics differ in teenagers compared with adults, and bone mass accrual is even more dependent on estrogen and IGF-1 in younger than older women who have already achieved peak bone mass.

(ii) Bone age (BA) \geq 14 years: 98% of adult height is achieved at a BA of 14 because only 2% of growth potential persists at a BA of 14 years. Thus, to avoid potential stunting of growth potential with estrogen replacement, we have chosen to include girls with BA of \geq 14 years.

(iii) BMI between 10th-90th percentiles for age, or BMI of at least 85% of ideal BMI

(iv) Amenorrhea (for AA): absence of menses for \geq three months (74) within a period of oligomenorrhea (cycle length $>$ six weeks) for \geq six months, or absence of menarche at ≥ 16 years

(v) Eumenorrhea (EA and controls): \geq nine menses (cycle length 21-35 days) in preceding year.

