(vi) Non-athlete healthy controls will be eligible if weight bearing exercise activity is less than two hours a week and if they are not participating in organized team sports.

(vii) Endurance athletes: severity of low BMD and menstrual dysfunction differ by kind of exercise and activity. For example, runners have a higher prevalence of menstrual irregularity than swimmers and cyclists (131). By limiting enrollment to endurance athletes, we will eliminate variability from the type of activity. Endurance training is defined as ≥ 4 h of aerobic weight-bearing training of the legs or specific endurance training weekly, or ≥ 20 miles of running weekly for a period of ≥ 6 months in the last year. These criteria were developed following discussions with [name], an expert in exercise physiology and a study consultant, and his interactions with athletic coaches at Boston University. [name] was until recently a Professor in the Department of Health Sciences at the Sargent College of Health & Rehabilitation Sciences, Boston University, a first tier school for competitive athletic activities involving endurance training. [name] has been studying athletes and conducting maximal exercise testing in Sargent College for the past 28 years on populations that include exercising young women. Our criteria differ from those used by a group from Sweden (74) that examined women 16-35 years old. This group specified endurance training as ≥ 6 h of aerobic weight-bearing training of the legs or ≥ 43.75 miles of running weekly for at least 6 months in the last year or 6 h of specific endurance training weekly. These criteria were considered excessive and unrealistic for girls 14-21 years old by [name] and the coaches at Boston University, and the criteria modified as described. Cyclists and swimmers will be excluded because their training does not include true weight-bearing activities. Rowers (but not coxswains) and gymnasts will also be excluded given that these activities have been associated with a preservation of bone density even when associated with amenorrhea likely consequent to differences in the nature of weight bearing and impact. Track and cross-country runners will be included. [name] will review screening information to confirm eligibility.

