- (iii) Endurance athletes engaged in sports that involve weight bearing training of the legs. Severity of low BMD and gonadal dys-function may differ by type of exercise (131). By limiting enrollment to weight bearing endurance athletes, we will eliminate variability from type of activity. Endurance training is defined as \geq 4h of aerobic weight-bearing training of the legs or specific endurance training weekly, or \geq 20 miles of running weekly for \geq 6 months in the last year. Cyclists, rowers and swimmers will not be included because these activities do not involve lower extremity weight bearing. Gymnasts will not be included (not an endurance sport),
- (iv) Non-athletes will be eligible if weight bearing exercise activity is $<$ 2h a week and they are not participating in organized team sports.

Exclusion Criteria:

- (i) Use of medications affecting bone metabolism (washout period of 3 months prior to enrollment if medically permissible to discontinue these)
- (ii) Conditions other than endurance training that may cause hypogonadism or low bone density
- (iii) High TSH, FSH or prolactin
- (iv) Standard MRI exclusion criteria such as presence of pacemaker, intracranial metal clips, severe claustrophobia

Briefly describe study procedures. Include any local site restrictions, for example, "Subjects enrolled at Partners will not participate in the pharmacokinetic portion of the study." Describe study endpoints.

Over the proposed 5-year investigation, 145 teenage girls and young adults 14-25 years old with AA, 42 EA and 42 non-athletic controls will be studied. Eligibility will be assessed at the screen, and the study will include a baseline visit and follow up visits at 3, 6, 9 and 12 months. The baseline visit will occur within 8 weeks of the screen. EA and controls will be followed without intervention (except elemental calcium and vitamin D) for 12 months.

For Specific Aim 3 we anticipate screening 2 times the number of athletes that we will eventually enroll in the study to obtain 145 eligible AA adolescents. In addition, for Specific Aims 1 and 2, we anticipate screening 2 times the number of EA (n=42) and non-athletic controls (n=42) required for this section of the study (total subjects to be screened= 458).

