For Specific Aims 7 and 8 we anticipate screening (over the phone) 2 times the number of athletes that we will eventually enroll in the study to obtain 40 eligible male endurance athletes. In addition, we anticipate screening (over the phone) 2 times the number of healthy male non-athletes in order to obtain 20 eligible non-athletic controls (total male subjects to be screened = 120).

Screening Visit: Informed consent will be obtained from parents and assent from subjects $<$ 18y old, and informed consent from subjects \geq 18y. Eligibility will be determined at this visit, which will include:

- (a) History (including medications, current and past mental health issues), physical examination, height, weight, BMI, waist, hip circumference
- (b) Screening labs: complete blood count, ALT, AST, TSH, FSH (to rule out premature/primary ovarian failure), 30 cc of blood will be drawn, frozen, and stored for later analysis.
- (c) The Bouchard 3-day activity record (129) (to confirm criteria for endurance training are met).
- (d) Bone age (wrist and hand X-ray) and bone density using DXA: spine, hip and total body.
- (e) Stratification of AA subjects during randomization will be based on Z-scores at the spine (\leq -1 or $>$ -1). Body composition will be assessed by DXA. AA dancers will be randomized using a separate randomization template than AA non-dancers.

(f) Two subtests, Vocabulary and Matrix Reasoning, from the Weschler Abbreviated Scale of Intelligence (WASI), a Color-Word Interference Test subtest from the Delis Kaplan Executive Functioning Scale (DKEFS), and the California Verbal Learning Test (CVLT).

The DXA, bone age and cognitive tests will be completed at the screening visit, in between the screening and baseline visits or at the baseline visit.

Baseline Study Visit: This visit will occur within eight weeks of the screen and will include:

- (a) History and physical examination with anthropometric measurements
- (b) Eating disorder questionnaires (EDI-2), Three-Factor Eating Questionnaire-R18 (TFEQ), and a 4-day food diary (to assess caloric intake)
- (c) Resting energy expenditure (REE) using indirect calorimetry
- (d) Salivary cortisol at 11 p.m.
- (e) Fasting (or 2 hour post-prandial) blood samples for leptin, adiponectin, ghrelin, PYY, IGF-1, insulin, estradiol, testosterone, SHBG, FSH and LH, bone turnover markers (PINP and N-telopeptide).
- (f) Fasting (or 2 hour post-prandial) calcium, phosphorus and 25(OH) vitamin D

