The first step in data analysis is to determine models for longitudinal data collected. These models are usually based on our knowledge of how these data behave and details of the study. These models can also be checked to see whether they fit the data by viewing data for each patient without regard to patient group. For instance, BMD can be assumed to increase linearly over the study duration. We hypothesize that this linear increase will be slowest in untreated AA patients and intermediate in those on oral estrogen, and the smallest effect size would be the difference between groups randomized to transdermal versus oral estrogen. We would check this linearity by looking at data from individual patients and checking that actual measurements are normally distributed around the patient's linear trajectory by looking at residuals (difference between observed value and trend line). It is possible that in some cases linearity and normality might hold after a log or other transformation. If linearity holds for actual or transformed values, variables will be analyzed by mixed model ANOVA, a common method for analyzing longitudinal data. One advantage of this method is that it allows us to use data from subjects that drop out early. The linear model is appropriate for BMD, but will not be appropriate for variables that may be relatively constant during treatment. These might include measurements of bone turnover and hormones. These would be modeled assuming that each patient has a constant level. After examining how well the assumed model fits the data, repeated measures ANOVA will be used for analysis. In this model there is a fixed treatment term of primary interest. Measurements at each time are assumed to be a multivariate observation with an unspecified variance covariance matrix.

Power calculation for primary endpoint: Power analysis is based on the primary endpoint, i.e. average change in BMD over one year in a randomized trial comparing mean change in spine BMD in young women 14-25 years old with AA randomized to transdermal estrogen versus oral estrogen or no therapy for one year. Girls with AA will be stratified based on spine BMD Z-scores (≤ -1 or > -1).

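### The sample is expected to contain dancers as well as other endurance athletes, yet neither document accounts for dance in the non-randomised AA-EA bone comparisons, so confounding by activity type is possible there

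*Protocol*

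**What the plan says.** The protocol controls for sport by restriction. Research Design and Methods explains: "Because different kinds of physical activity have different effects on bone metabolism, we will enroll only endurance athletes". Inclusion Criterion (vii) for females notes that both low BMD and menstrual dysfunction vary with the kind of exercise, and concludes: "By limiting enrollment to endurance athletes, we will eliminate variability from the type of activity". The male Inclusion Criterion (iii) repeats the claim: "By limiting enrollment to weight bearing endurance athletes, we will eliminate variability from type of activity".

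Criterion (vii) defines endurance training as at least 4 "h of aerobic weight-bearing training of the legs or specific endurance training weekly", or at least 20 miles of running a week, for six months or more in the last year. It names track and cross-country runners as included and cyclists, swimmers, rowers and gymnasts as excluded. Dancers are in neither list.

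Dancers appear once, in Screening Visit item (e). After giving the spine Z-score stratification, it adds: "AA dancers will be randomized using a separate randomization template than AA non-dancers".

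The SAP (Power calculation for primary endpoint) gives only the Z-score stratum: "Girls with AA will be stratified based on spine BMD Z-scores". It names no sport or dance term in its models.

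**The concern.** By the protocol's own account, activity type is related to menstrual function, which separates AA from EA, and to bone, which is the outcome. A variable related to both is a candidate confounder of the AA-EA contrast. Restriction was meant to remove it, but a separate randomisation template makes sense only if dancers are expected among AA and are thought different enough to need balancing.

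The template balances dancers across transdermal estradiol, oral estradiol and no treatment, so the randomised comparison, including the primary endpoint, is protected. EA are not randomised, and neither document states a way of making AA and EA comparable on dance.

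At stake is the reading of Aims 2 and 4. If the groups differ in their mix of dancers and runners, part of a difference in bone structure or strength attributed to amenorrhea could reflect loading type, or a true deficit could be partly hidden.

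**Working it through.** The plan has no figure of its own to reproduce here. The check has two parts.

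**The texts side by side.** Criterion (vii) rests on a single broad activity class. Its weekly-hours limb does not require running, so a dancer could satisfy it. Item (e) confirms that dancers are expected in AA and handled separately. The two can be reconciled on eligibility, but not on the claim that variation by activity type has been eliminated.

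**Scale, under assumptions.** Inputs from the protocol: 145 AA and 42 EA overall; 100 AA and 36 EA in the X-treme CT subset at baseline; 66 AA and 22 EA for baseline FEA. Inputs not in the documents, and so assumed: the gap in dancer share between AA and EA (10 to 30 percentage points) and the dancer versus non-dancer difference in the bone measure (0.25 to 1.0 SD).

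- Bias in SD units: b = (dancer share in AA − dancer share in EA) × (dancer − non-dancer difference in SD).
- Standard error of the AA-EA difference in SD units: se = √(1/n_AA + 1/n_EA).
- False-positive rate of a two-sided 5% z-test when amenorrhea has no effect: 1 − Φ(1.96 − b/se) + Φ(−1.96 − b/se).

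Central illustration, 145 AA against 42 EA: b = 0.20 × 0.5 = 0.10 SD; se = √(1/145 + 1/42) = 0.175; b/se = 0.571; rate = 0.0824 + 0.0057 = 0.088.

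| AA vs EA | Share gap | Dancer difference | Bias | False-positive rate |
|---|---|---|---|---|
| 145 vs 42 | 0 | any | 0 | 5% |
| 145 vs 42 | 10 points | 0.25 SD | 0.025 SD | 5.2% |
| 145 vs 42 | 20 points | 0.5 SD | 0.10 SD | 8.8% |
| 145 vs 42 | 20 points | 1.0 SD | 0.20 SD | 20.7% |
| 145 vs 42 | 30 points | 1.0 SD | 0.30 SD | 40.2% |
| 100 vs 36 (se 0.194) | 20 points | 0.5 SD | 0.10 SD | 8.1% |
| 66 vs 22 (se 0.246) | 20 points | 0.5 SD | 0.10 SD | 6.9% |

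The bias in SD units does not depend on sample size. The false-positive rate is lower in the subsets only because their standard errors are larger.

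**Level or change.** The formula applies to a difference in level, as in the baseline comparisons. A constant dancer-runner difference cancels when each participant's 12-month change is taken. For change endpoints the second factor must be a dancer-runner difference in the rate of change, and the documents give no evidence of one.

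**The case against.** The case on the other side is substantial.

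- **Eligibility.** A reader might infer that dancers are enrolled in breach of the endurance criterion. The documents do not support this. The weekly-hours limb can admit a dancer, the runners named are not said to be the only sport allowed, and the reasons given for excluding the four named sports are not applied to dancers. This part of the objection stands.
- **Asymmetry.** A reader might infer that dancers are concentrated in AA. Criterion (vii) covers EA as well, and dancers surface only in the AA randomisation text because only AA are randomised. No imbalance is shown. This stands too, but balance is not secured either.
- **Males.** A reader might extend the point to the male-female comparison in Aim 8. The male criteria use essentially the same definition and are as silent on dancers as the female ones, so nothing marks a difference. That extension depends on the mix actually observed.
- **Change endpoints.** The Aim 2 accrual comparison concerns change, where a stable difference in level cancels. This stands, and limits the concern mainly to baseline microarchitecture and FEA strength.
- **Size and direction.** Every bias input is assumed. If dance loading preserved bone and dancers were over-represented in AA, the bias would hide an AA deficit rather than create one.
- **Unseen analysis detail.** The SAP says that sub-aim analyses are set out in the grant, which is not among the documents. Its silence on covariates is weak evidence that none are planned.

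What survives is narrow: the protocol identifies activity type as a source of variation, expects a second type, claims to have eliminated the variation, and states protection for the randomised arms only.

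**Conclusion.** The statement that variation by type of activity will be eliminated does not hold for a sample in which AA dancers need their own template. Confounding of the non-randomised AA-EA bone contrasts is possible but not shown. It bears mainly on baseline microarchitecture and FEA strength in Aims 2 and 4. It reaches the 12-month changes only if accrual differs by activity, and Aim 8 only if the observed mix of male and female athletes differs.

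Size and direction cannot be taken from the documents. Across the assumed ranges the effect runs from negligible (0.025 SD, 5.2% false positives) to material (0.30 SD, 40.2%), and it vanishes with equal dancer shares. The calculation also assumes a simple two-group z-test with common variance and no other imbalance.

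The randomised comparison of estradiol routes and no treatment is not in question. This is a low-cost improvement to the observational aims.

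**What to change.** 1. Record dancer or non-dancer status for EA as well as AA, and for male athletes if any dance. For AA it must already be known in order to use the template.
2. Report the number of dancers in each group.
3. Include dancer status as a factor in the AA-EA bone models.
4. Repeat the main AA-EA bone comparisons in non-dancers only. This matters most if EA contains few or no dancers, because the model then has little basis for separating dance from amenorrhea.
5. For the Aim 8 athlete comparisons, add the factor only if the counts show a different mix.
6. In the female and male endurance criteria, replace *eliminate* with *reduce*.

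The cost is one recorded field, one degree of freedom per model, and a somewhat smaller sample in the sensitivity analysis. No change to recruitment targets or to the randomisation is needed.

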**PARTNERS HUMAN RESEARCH COMMITTEE
PROTOCOL SUMMARY**

Answer all questions accurately and completely in order to provide the PHRC with the relevant information to assess the risk-benefit ratio for the study. Do not leave sections blank.

PRINCIPAL/OVERALL INVESTIGATOR

[name].

PROTOCOL TITLE

Fat Mediated Modulation of Reproductive and Endocrine Function in Young Athletes

NCT00946192

FUNDING

NIH

VERSION DATE

December 4, 2014

SPECIFIC AIMS

Concisely state the objectives of the study and the hypothesis being tested.

Specific Aim 1: We will test the hypothesis that in adolescent athletes

- (i) Suboptimal energy availability preferentially lowers fat mass with sparing of lean mass**
- (ii) Lower fat mass leads to altered levels of adipokines (lower leptin, higher adiponectin) and fat regulated hormones (higher ghrelin, PYY), and**
- (iii) Altered levels of adipokines and fat regulated hormones determine hypogonadism and decreased gonadotropin pulsatility.**

In a cross-sectional study, we will specifically investigate whether (i) adolescent athletes in a state of low energy availability have lower fat mass than those with optimal energy availability, (ii) lower fat mass results in alterations in adipokines (decreases in leptin and increases in adiponectin) and fat regulated hormones (increases in ghrelin, PYY), and whether (ii) LH pulsatility patterns are predicted by pulsatility patterns of hormones produced (leptin, adiponectin) or regulated (ghrelin, PYY) by fat.

Specific Aim 2: We will test the hypothesis that in adolescent athletes

- (i) Bone mass accrual rates (assessed by DXA) are markedly decreased in AA compared with EA and controls**
- (ii) Bone microarchitecture at the ultradistal radius and leg (assessed by X-treme CT) is abnormal in AA with decreased trabecular thickness (TbTh) and increased separation (TbSp); deterioration occurs over time in AA compared to EA and controls who demonstrate increases in healthy bone, and**
- (iii) Independent of hypogonadism, adipokines and fat regulated hormones are critical determinants of bone mass accrual rates and bone microarchitecture**

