In a prospective observational study, we will compare changes in bone density, trabecular volume, trabecular thickness, number and separation over 12 months in a subset of AA versus EA and controls, and will investigate in a regression model whether altered levels of adipokines (lower leptin, higher adiponectin) and fat regulated hormones (higher ghrelin, PYY) determine lower bone mass accrual rates and altered bone structural parameters independent of gonadal status

Specific Aim 3: In a randomized controlled trial, we will test the hypothesis that in adolescent AA, compared to oral estradiol or no treatment, transdermal estradiol replacement will

- (i) Increase bone mass accrual rates (DXA)**
- (ii) Increase TbTh and bone trabecular volume (X-treme CT), and**
- (iii) Not affect endurance capacity**

In a randomized controlled trial, adolescent AA will be randomized to transdermal estradiol in replacement doses, oral estradiol or no therapy for 12 months. Effects on bone accrual rates and endurance capacity will be assessed in comparison to EA and controls. In a subset of AA, we will examine effects of estradiol replacement on bone structural parameters compared to EA and controls.

Specific Aim 4: We will test the hypothesis that in athletes 14-25 years old

- (i) Bone strength [as assessed using Finite Element Analysis] is lower in adolescent and young adult AA compared with EA and sedentary controls at baseline and decreases prospectively over one-year in AA, whereas bone strength increases in EA over the same duration.**

Specific Aim 5: We will test the hypothesis that in athletes 14-25 years old

- (i) Greater visceral adipose tissue (VAT) and lower subcutaneous adipose tissue (SAT) are associated with lower bone density, impaired microarchitecture and lower bone strength, and that**
- (ii) Greater marrow fat is associated with lower bone density, impaired microarchitecture and lower bone strength.**

Specific Aim 6: We will test the hypothesis that in amenorrheic athletes 14-25 years old

- (i) **Transdermal estradiol, compared to oral estradiol or no treatment will increase bone strength to approximate that in controls, with decreases in marrow fat and no changes in regional body composition.**

Specific Aim 7: We will test the hypothesis that in adolescent and young adult male athletes

- (iv) **Suboptimal energy availability and an energy deficit state preferentially lower fat mass with sparing of lean mass**

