- (b) Fasting (or 2 hour post-prandial) blood samples for IGF-1, estradiol, testosterone, SHBG and LH, bone turnover markers (PINP and N-telopeptide).

Male Study Visit:

- (a) History and physical exam (H&P)
- (b) 7-8 AM Hormones: TSH, FSH, LH, testosterone, SHBG, estradiol, IGF-1, leptin, ghrelin (total), PYY (total),
- (c) 11 PM salivary cortisol (to be mailed back);

- (d) Calcitropic Measures and Markers of Bone Turnover: calcium, phosphorus, 25(OH) vitamin D, 1,25(OH)₂ vitamin D, PTH; PINP and CTX.
- (e) Activity Assessment: Bouchard 3-day activity record (129). Habitual activity will be further assessed using a standardized exercise questionnaire, which provides a good estimate of past year physical activity (173, 199),
- (f) 4-day food diary to assess caloric intake (NDS, version 4, Minneapolis, MN) and determine standard macronutrient intake,
- (g) Eating disorder questionnaire (EDI-2) (186), Three-Factor Eating Questionnaire-R18 (TFEQ),
- (h) Resting energy expenditure (REE) using indirect calorimetry,
- (i) VO₂ max and handgrip strength,
- (j) BMD: Lumbar spine, hip, radius, whole body areal BMD will be measured by DXA,
- (k) Body Composition: Whole body DXA will be used to assess fat and lean mass. In a subset of 10 athletes and 10 non-athletes, we will use MRI to assess SAT, VAT, thigh muscle area and marrow fat, (198) Bone microarchitecture and strength will be determined at the ultradistal radius and distal tibia using HR-pQCT (Xtreme CT, Scanco Medical AG). Bone strength will be determined using FEA of HR-pQCT scan data (187).

DNA testing:

We may ask subjects to participate in DNA testing via a saliva collection and/or blood collection at some point during this study in order to determine if there is a genetic basis for the hormonal changes seen in non-menstruating athletes. During one of the 6 visits for the “Fat Mediated Modulation of Reproductive and Endocrine Function in Young Athletes” study, we may draw 50cc (slightly more than 3 tablespoons) of blood for DNA testing, and may also ask for a sample of saliva for DNA testing. This will be an optional portion of the study, with a separate section of the consent forms to address this.

MRI:

We would like to assess SAT, VAT, thigh muscle area and marrow fat of AA prior to treatment and EA and non-athlete controls at some point during their 1 year study enrollment using MRI.

Finite Element Analysis:

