Subjects will complete all screening and baseline procedures at this visit. The subject will be consented and a complete medical history and physical exam will be performed before continuing with further study procedures. If subject is found to have any health concern or is found to meet any exclusion criterion during the history and physical, further study components will be canceled. Following this portion of the visit, the subject will complete the rest of the study procedures occurring at the screening and baseline visit, including:

- (a) Screening labs: complete blood count, K, ALT, AST, TSH, FSH (to rule out premature/primary ovarian failure), 30 cc of blood will be drawn, frozen and stored for later analysis
- (b) Fasting (or 2-hr post prandial) calcium, phosphorus and 25(OH) vitamin D
- (c) Bone age (wrist and hand X-ray) and bone density using DXA: spine, hip and total body.
- (d) The Bouchard 3-day activity record (129) (to confirm criteria for endurance training are met).
- (e) Eating disorder questionnaires (EDI-2), Three-Factor Eating Questionnaire-R18 (TFEQ), and a 4-day food diary (to assess caloric intake)
- (f) Two subtests, Vocabulary and Matrix Reasoning, from the Weschler Abbreviated Scale of Intelligence (WASI), a Color-Word Interference Test subtest from the Delis Kaplan Executive Functioning Scale (DKEFS), and the California Verbal Learning Test (CVLT).
- (g) Resting energy expenditure (REE) using indirect calorimetry
- (h) Indirect calorimetry and handgrip strength. This exam will be performed at the Clinical Research Center at Massachusetts General Hospital or at the Charlestown Navy Yard site.
- (i) Bone microarchitecture at the ultradistal radius and leg (non-dominant) will be assessed using X-treme CT in a subset of 100 (~33 in each randomization group) AA, 36 EA, 36 controls

- sometime between the screening and baseline visits or at the baseline visit. Finite element analysis (FEA) will also be performed.
- (j) MRI (regional fat and muscle) assessment.
 - (k) Salivary cortisol at 11 p.m. to be sent back to MGH

For the amenorrheic athletes, subjects will be randomized upon receiving results from the DXA scan, and verifying eligibility based upon the lab results and bone age x-ray. Subjects will start study medication as soon as possible.

Early Termination Visit: This will include procedures performed at the 12 month visit. Subjects will be asked to return unused medications and all questionnaires.

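### In female subjects ghrelin and PYY may be sampled fasting or 2 hours after an undefined meal, and the plan neither records the state, holds it constant within a subject, nor adjusts for it

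*Protocol*

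**What the plan says.** The Protocol's Baseline Study Visit, item (e), sets the sampling condition for the hormone panel in women: "Fasting (or 2 hour post-prandial) blood samples for leptin, adiponectin, ghrelin, PYY, IGF-1, insulin, estradiol, testosterone, SHBG, FSH and LH". Item (f) of the follow-up visits at 6 and 12 months repeats the same either/or rule: "Fasting (or 2 hour post-prandial) blood samples for leptin, adiponectin, ghrelin, PYY, IGF-1, insulin". For women who travel far, the Combined Screening and Baseline Visit inherits it, since "Subjects will complete all screening and baseline procedures at this visit".

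Ghrelin and PYY have named roles in the Specific Aims. In Aim 1(ii) they are outcomes: "Lower fat mass leads to altered levels of adipokines (lower leptin, higher adiponectin) and fat regulated hormones (higher ghrelin, PYY), and". Aim 1(iii) treats altered hormone levels as determinants of hypogonadism. In Aim 2 they are regressors; the question is whether altered adipokines and "fat regulated hormones (higher ghrelin, PYY) determine lower bone mass accrual rates and altered bone structural parameters independent of gonadal status".

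The SAP (Biostatistical analysis) expects hormones to be roughly constant within a patient during treatment. It analyses them by repeated measures ANOVA with a fixed treatment term and an unspecified covariance matrix. No term for prandial state is named. The SAP also says that the analysis of specific sub-aims is described in the grant, which is not among the documents.

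**The concern.** The rule lets two sampling conditions stand for one variable, both between women and between visits of the same woman. If a meal shifts ghrelin or PYY, the two conditions do not measure the same quantity. A woman sampled fasting at baseline and after a meal at 6 months would then show a change that is not biological. A constant-level model would absorb this as noise or, if it were patterned by group or visit, as effect.

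The stakes lie in the hormone aims. Where the hormone is an outcome, mixed states reduce precision. Where it is a regressor, they pull slopes towards zero. If the groups differ in how often they are sampled after a meal, a group difference can appear that has nothing to do with fat mass or gonadal status. If the state is not recorded, it cannot be reliably recovered at analysis.

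**Working it through.** **Is there a plan figure to reproduce?** No. No sample size, power or alpha in either document depends on the prandial state of a hormone sample.

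**Text check.** The baseline, combined, 3/9-month, 6/12-month and male visit lists and the whole SAP were searched for five things:
- a single required state: none for the female hormone draws;
- a defined meal: none; only the 2-hour interval is fixed;
- the same state across a subject's visits: not required;
- recording of the state: not required;
- a stratum or covariate for the state: none in the SAP.

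**Inputs for the illustration.**
- D, the shift in mean between states, in within-state SDs: not in the documents; assumed 0.25, 0.5 or 1.0.
- p, the share of draws taken after a meal: not in the documents; assumed 10 to 50%.
- Difference in p between two groups: not in the documents; assumed 20 points.
- Group sizes: 145 AA, 42 EA and 42 controls (Protocol, study procedures), used for illustration only.

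**Noise.** If the state is unrelated to the true level, the variance is multiplied by V = 1 + p(1 − p)D². The SD is multiplied by √V. Where the hormone is the regressor, a correlation is multiplied by 1/√V and a simple regression slope by 1/V.

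| D | p | V | SD × | correlation × | slope × |
|---|---|---|---|---|---|
| 0.25 | 10% | 1.0056 | 1.003 | 0.997 | 0.994 |
| 0.25 | 50% | 1.0156 | 1.008 | 0.992 | 0.985 |
| 0.5 | 10% | 1.0225 | 1.011 | 0.989 | 0.978 |
| 0.5 | 50% | 1.0625 | 1.031 | 0.970 | 0.941 |
| 1.0 | 10% | 1.0900 | 1.044 | 0.958 | 0.917 |
| 1.0 | 50% | 1.2500 | 1.118 | 0.894 | 0.800 |

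Example: D = 1 and p = 0.5 give V = 1 + 0.5 × 0.5 × 1 = 1.25, and √1.25 = 1.118.

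Where the hormone is the outcome, take 42 against 42 and a true difference of 0.62 SD, chosen to give about 80% power. Power is 81% with one state. With p = 50% it is 79% at D = 0.5 and 72% at D = 1.0.

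**Bias.** If the post-prandial shares differ, the false group difference is b = D × (pA − pB). The rejection rate of a nominal two-sided 5% test with no true difference is approximately 1 − Φ(1.96 − b/SE) + Φ(−1.96 − b/SE). Here SE = √(1/n₁ + 1/n₂) with SD 1, which gives √(2/42) = 0.218 for 42 against 42 and √(1/145 + 1/42) = 0.175 for 145 against 42.

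| D | b at 20 points | 42 vs 42 | 145 vs 42 |
|---|---|---|---|
| 0.25 | 0.05 SD | 5.6% | 5.9% |
| 0.5 | 0.10 SD | 7.4% | 8.8% |
| 1.0 | 0.20 SD | 15% | 21% |

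If the shares are equal across groups, b = 0 and only the noise remains.

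**The case against.** The strongest reply is that the effect may be negligible. Every number above rests on assumed values. At a shift of 0.25 SD the SD rises by less than 1% and a 20-point imbalance gives 0.05 SD. Even at 0.5 SD with half the draws post-prandial, power falls only from 81% to 79%. Material harm needs a shift near 1 SD or unequal shares, and the documents do not show that the groups differ in share. The 2-hour interval is also a partial standardisation, and an adjustment may be described in the grant. All of this stands as a limit on size. It does not remove the gap: an adjustment in the grant would need the state to be recorded, and neither document requires that.

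Some wider readings are tempting but unsupported.
- A reader might extend the point to the male athletes of Aim 7. Their draw is listed separately as "7-8 AM Hormones: TSH, FSH, LH, testosterone, SHBG, estradiol, IGF-1, leptin, ghrelin (total), PYY (total". It fixes the clock time and has no either/or rule; its silence on fasting is a different gap.
- A reader might add insulin, which is in the same female panel. No aim names it; the fat-regulated hormones are ghrelin and PYY, with cortisol added in Aim 7.
- A reader might cite the 3- and 9-month visits: "Fasting (or 2 hour post-prandial) blood samples for IGF-1, estradiol, testosterone, SHBG and LH". The rule is the same, but ghrelin and PYY are not drawn then.
- A reader might say that slopes are weakened throughout Aim 1. In Aim 1(ii) the hormones are outcomes, where random noise lowers precision without attenuating the slope. The analysis spelled out for the last part of Aim 1 uses pulsatility patterns, which a single draw cannot give; only the wording about levels in Aim 1(iii) brings the single draw in.

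**Conclusion.** The point holds for ghrelin and PYY in female subjects at baseline, 6 and 12 months. Two sampling states are allowed, and neither document requires one state, consistency within a subject, recording, or adjustment.

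Under the assumed ranges the SD rises by about 0 to 12%, with the matching loss of precision in Aim 1(ii). Slopes are attenuated in Aim 2, and in Aim 1(iii) so far as it uses single-draw levels. A false group difference of 0.05 to 0.20 SD arises only if post-prandial shares also differ by 20 points. That meals shift these hormones at all is an assumption here, not a figure in the documents.

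A reader might infer that the trial's main result is at risk, or that bias is established. Neither follows. The primary endpoint is change in spine BMD, which this rule does not touch, and bias is possible rather than shown. This is a limited weakness in the hormone aims, worth correcting because the correction is cheap.

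**What to change.** - At each female ghrelin and PYY draw (baseline, 6 and 12 months, including combined visits), record prandial state and time since the last meal.
- Keep each subject in the same state across her visits, preferably fasting where feasible. Fasting need not be mandatory, given the travel difficulties the Protocol describes for some subjects.
- In the SAP, include prandial state as a covariate in the ghrelin and PYY analyses, both as outcomes and as regressors. If the grant already has such a term, bring it into the SAP.
- Add a fasting-only sensitivity analysis. The covariate assumes the same shift in every group, and an undefined meal makes that uncertain; the fasting-only result checks it with fewer subjects.

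Cost: one case report form field, one model term and some scheduling effort. No sample size or primary analysis changes.
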